4. STUDY DESIGN

4.1. Overall Design

[figure not shown]
- This is a randomized, open-label (sponsor blind), active-controlled, parallel-group, multi-center study in subjects with anemia associated with CKD who are not regularly using routine erythropoiesis-stimulating agent (ESA) users and who are initiating dialysis.
- The study will comprise three study periods: a screening period (2 weeks*), a 52-week active treatment period, and a follow-up period (4-6 weeks) ([Figure 1](#)). Weeks 28-52 are defined as the efficacy evaluation period (EP) for the *primary* efficacy comparison.

* Screening period can be extended by an additional 4 weeks for ultrasound examination, IV iron supplementation and/or vitamin B12 treatment as needed.

- A central randomization approach will be used to protect the trial from potential for selection bias due to the open-label design. All subjects will be treated to achieve and maintain an Hgb within a range of 10-11 g/dL.
- Limited ESA use is allowed around the time of dialysis initiation only (see [Section 5.2](#) for definition of “limited use”).
- The treatment period consists of:

- The stabilization period, defined as the period from Day 1 to Week 28 during which randomized treatment will be dose titrated to achieve the appropriate Hgb target.
 - The evaluation period (EP), defined as the period from the end of the stabilization period (Week 28) to Week 52 (titrations may also occur during this treatment period), to assess safety and efficacy.
- Subjects will be stratified by dialysis type (hemodialysis [HD] or peritoneal dialysis [PD]) and by whether their dialysis start is planned or unplanned (urgent).
 - Following stratification, subjects will be randomized 1:1 to receive daprodustat or rhEPO (darbepoetin alfa); all randomized treatments (Section 6.1) will be supplied by GSK.
 - To ensure consistency of treatment across the study there are protocol-mandated algorithms for dose adjustments of daprodustat and rhEPO (Section 6.2), iron management (Section 6.10) and anemia rescue therapy (Section 6.11)
 - An overview of the study design is provided in Figure 1.

Figure 1 Study Schematic

* Screening period may be extended by an additional 4 weeks for ultrasound examination, IV iron supplementation and/or vitamin B12 treatment as needed.

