10.4. Appendix 4: Treatment States and Phases

10.4.1. Treatment Phases

Assessments and events will be classified according to the time of occurrence relative to treatment start and stop dates and last non-zero dose date (see Section 10.6.1).

10.4.1.1. Treatment States for Hgb, Iron Parameters, IV Iron Dose Endpoints, Iron Use Summaries, Transfusion and PRO Data

Treatment Phase	Definition
Pre-Treatment	Date ≤ Treatment Start Date
On-Treatment	Treatment Start Date < Date ≤ Treatment Stop Date + 1 day
Post-Treatment	Date > Treatment Stop Date + 1 day
Post-Randomization	Randomization Date < Date

NOTES:

If the treatment stop date is missing and the treatment start date is non-missing and Date > Treatment Start Date, then the assessment will be considered to be On-Treatment

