
 • Transfusion Events per 100 PY = (100 * number of on-treatment RBC or whole blood transfusion events during the evaluation period) / Patient Years (PY) • Transfusions per 100 PY = (100 * number of on-treatment RBC or whole blood transfusions during the evaluation period) / Patient Years (PY) • Units per 100 PY = (100 * number of on-treatment RBC or whole blood transfusion units during the evaluation period) / Patient Years (PY)
Randomization to Week 52

 • Only transfusion events with a start date from the date of randomization to the date of the week 52 visit will be included • Patient Years (PY) = (cumulative total time from date of randomization to the date of the week 52 visit, for subjects who did not withdraw from randomized treatment prior to week 52 + cumulative time from date of randomization to the date of withdrawal from randomized treatment, for subjects who withdrew from randomized treatment prior to week 52) / 365.25 • Transfusion Events per 100 PY = (100 * number of on-treatment RBC or whole blood transfusion events from the date of randomization to the date of the week 52 visit) / Patient Years (PY) • Transfusions per 100 PY = (100 * number of on-treatment RBC or whole blood transfusions from the date of randomization to the date of the week 52 visit) / Patient Years (PY) • Units per 100 PY = (100 * number of on-treatment RBC or whole blood transfusion units from the date of randomization to the date of the week 52 visit) / Patient Years (PY)
Time to First On-Treatment RBC or Whole Blood Transfusion

 • Event Date = Start date for the first on-treatment RBC or whole blood transfusion received after treatment start date • Censoring Date = date of stopping randomized treatment for subjects who stopped randomized treatment, or date of study completion for subjects who did not stop randomized treatment • Time to event (days) = date of event – treatment start date + 1 • Censored time (days) = censoring date – treatment start date + 1

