
 • Person years (PY) = (cumulative total time to event date, for subjects who received at least one on-treatment RBC or whole blood transfusion + cumulative total of censoring time for subjects who did not receive at least one on-treatment RBC or whole blood transfusion) / 365.25 • Incidence rate per 100 PY = (100 * number of subjects who received at least one on-treatment RBC or whole blood transfusion) / person years • Absolute rate difference (per 100 person years) = daprodustat incidence rate (per 100 person years) – darbepoetin alfa incidence rate (per 100 person years)
Time Period for On-Treatment Transfusions

 • The period for capturing on-treatment transfusions begins on the treatment start date + 1 day. The end of this time period is defined as follows: 
 ○ For subjects continuing on study past the (treatment stop date + 1 day), use (treatment stop date + 1 day) ○ For subjects whose study withdrawal/completion date is on or before (treatment stop date + 1 day), use date of study withdrawal/completion

Model Specification

 Analysis of time to first RBC or whole blood transfusion will be performed using an analysis model identical to that described for the time to stopping randomized treatment due to meeting rescue criteria (Section 8.1.2). Analysis will include only transfusion occurring during the on-treatment period..
Model Results Presentation

 The model results presentation will be identical to the co-primary MACE model results, with the following exception: A single one-sided p-value for the test of superiority of daprodustat vs. darbepoetin alfa will be presented (i.e. there will be no test for non-inferiority). A Kaplan-Meier plot will be produced showing the survival function for time to first RBC or whole blood transfusion.

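### Time to first on-treatment transfusion censors treatment completers at study completion, which may fall 4–6 weeks after transfusions stop counting; rates may be 0 to about 10% too low

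*SAP*

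**What the plan says.** **Event.** SAP 10.6.3.4 takes as event date the "Start date for the first on-treatment RBC or whole blood transfusion received after treatment start date". The window for such transfusions ends as follows: "For subjects continuing on study past the (treatment stop date + 1 day), use (treatment stop date + 1 day". If study completion or withdrawal comes no later than that, its date ends the window instead. The model specification adds: "Analysis will include only transfusion occurring during the on-treatment period". SAP 10.4.1.1 gives the same limits for the on-treatment state of transfusion data: "Treatment Start Date < Date ≤ Treatment Stop Date + 1 day".

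**Censoring.** The same section censors subjects who stopped randomized treatment at the date of stopping. Everyone else is censored at the "date of study completion for subjects who did not stop randomized treatment". Person-years include the "cumulative total of censoring time for subjects who did not receive at least one on-treatment RBC or whole blood transfusion".

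**Calendar.** Protocol 4.1 describes "a 52-week active treatment period, and a follow-up period (4-6 weeks". Protocol Table 6 places the follow-up visit at Weeks 56–58.

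**Presentation.** "The model results presentation will be identical to the co-primary MACE model results", except that there is a single one-sided superiority p-value and no non-inferiority test.

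**The concern.** A time-to-event analysis needs the time at risk and the period for counting events to end on the same day. Here a treatment completer may stay in the risk set, and in the person-year denominator, after any transfusion has ceased to count. Such time is event-free by definition and carries no information about transfusion. At stake are the incidence rate per 100 person-years, the absolute rate difference and the tail of the Kaplan-Meier plot.

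The presentation rule is a separate, smaller matter. MACE is exploratory in this study (Protocol 9.4.4.1, SAP 8.2.2.4). It is reported with rates, confidence intervals and a Kaplan-Meier plot, and has neither a hazard model nor a non-inferiority test. The instruction therefore points to a layout that this SAP does not contain.

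**Working it through.** The documents give no transfusion rate, event count or power for this endpoint, so there is no planned figure to reproduce. The check compares the rules and then sizes the gap.

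**1. Where a treatment completer's time ends**

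| Quantity | End | Source |
|---|---|---|
| Transfusion can count as an event | Treatment stop + 1 day, or study completion/withdrawal if no later | SAP 10.6.3.4 |
| Censoring in time to first transfusion | Study completion | SAP 10.6.3.4 |
| Person-years for transfusion rates, randomization to Week 52 | Week 52 visit | SAP 10.6.3.4 |
| Time to rescue | Treatment stop; exceptions are never-treated subjects (randomization date) and treated subjects with a missing stop date (study conclusion date) | SAP 10.6.3.3 |

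Of these rules, only the second runs past the end of treatment for a completer with a known stop date.

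**2. Length of the gap.** It is about 0 days if completion is dated at Week 52, and 4–6 weeks (28–42 days) if it is dated at Weeks 56–58.

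**3. One event-free completer.** Added time is 4/52 = 7.7% to 6/52 = 11.5%. If everyone completes and events are negligible, the rate changes by the factor 365/(365 + 28) = 0.929, a fall of 7.1%, or 365/(365 + 42) = 0.897, a fall of 10.3%.

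**4. A whole arm, closed form.** Assume that a share c completes treatment and that the others average 26 weeks. Neither value is in the documents. True weeks per subject = 52c + 26(1 − c); counted weeks add c × f, where f is 4 or 6.

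| c | True | Counted, f = 4 | Rate | Counted, f = 6 | Rate |
|---|---|---|---|---|---|
| 0.6 | 41.6 | 44.0 | −5.5% | 45.2 | −8.0% |
| 0.7 | 44.2 | 47.0 | −6.0% | 48.4 | −8.7% |
| 0.8 | 46.8 | 50.0 | −6.4% | 51.6 | −9.3% |

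This gives follow-up time to every completer, including those already transfused, so it slightly overstates the effect within each row.

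**5. Simulation with events.** Assumptions: constant hazard; one-year transfusion probability of 5%, 15% or 30%; 0%, 15% or 30% stopping treatment uniformly before Week 28. The last value is the upper figure in Protocol 9.2.1. Compared with censoring at treatment stop + 1 day, the SAP rule lowers the rate by 5.1–6.7% when completion is 28 days after treatment stop and by 7.5–9.9% at 42 days. For example, at 15% probability and 15% stopping, about 16.3 per 100 person-years becomes about 15.3 or 14.8.

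**6. Treatment comparison.** With assumed one-year probabilities of 10% and 20%, and 20% stopping in each arm:

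- The absolute difference moves from −11.78 to −11.14 per 100 person-years at 28 days (11.14/11.78 = 0.946, a shrinkage of 5.4%). At 42 days it moves from −11.77 to −10.82 (0.919, a shrinkage of 8.1%).
- The rate ratio moves from 0.472 to 0.471, and from 0.473 to 0.470.
- With equal hazards but 15% against 30% stopping, the false difference is below 0.1 per 100 person-years (−0.06 and −0.07).
- In one simulated trial of 150 per arm, the Cox hazard ratio was identical with completers censored 1, 28 or 42 days after treatment stop. This is expected, because the partial likelihood uses risk sets only at event times and nearly all the added time lies after the last countable event.

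**The case against.** **Completion may mean Week 52.** Protocol 5.7 and SAP 10.7.1 count a subject as a completer on reaching the End of Treatment visit. SAP 3.2 lists study completion and final clinic visits as separate conditions, which fits completion preceding follow-up. If the date is recorded accordingly, there is no gap. This objection stands as a limit on the size. It does not remove the problem, because those passages define a status and the date comes from the Study Conclusion form. SAP 10.6.1 does not tie that date to a visit. Other uses lean towards follow-up: it ends cardiovascular follow-up (SAP 10.6.4.1), and it is the censoring date for post-randomization adverse events (SAP 10.6.4.3), which are collected to the Follow-up visit (SAP 10.4.1.4). None of this settles the date.

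**The completion clause may be only a fallback.** SAP 10.6.1 gives every treated subject a treatment stop date, so completers could be said to have stopped on that date, leaving the clause for missing dates. SAP 10.6.2.3 weakens this reading: it names a group who did not discontinue treatment and censors them at treatment stop. The SAP thus recognises completers as not having discontinued even though they have a stop date.

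**The consequence is small.** This stands. The endpoint is exploratory, was added in the SAP (2.1, Table 1), and lies outside the testing hierarchy (SAP 10.11.1.2).

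A reader might also infer that all transfusion results, or the treatment comparison itself, are biased. The documents do not support that. The transfusion rates from randomization to Week 52 already stop completers' time at the Week 52 visit, and the hazard ratio and rate ratio barely move.

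**Conclusion.** The rule is wrong as written, because it permits person-time that cannot contain an event. Its effect is conditional. The understatement is about zero if completion is dated at Week 52. If it is dated at Weeks 56–58, incidence rates are about 5–10% too low, with a similar proportional shrinkage of the absolute difference and a flat Kaplan-Meier tail. The range rests on assumed completion and transfusion rates. It would overstate the case to say that the reported rates will be too low, since the SAP leaves the completion date open. The hazard ratio and its p-value are essentially unaffected. This is a minor point on an exploratory endpoint, worth correcting because the correction is free.

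**What to change.** In SAP 10.6.3.4, set the censoring date for all treated subjects without an event to the earlier of treatment stop date + 1 day and study completion/withdrawal date. This matches the event window in the same section and makes the result independent of how sites date completion. It also removes a one-day mismatch for early stoppers, who are now censored at treatment stop although their transfusions count for one day more.

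Replace the co-primary MACE reference with the time-to-rescue presentation in SAP 8.1.2.2, which already supplies the hazard ratio, confidence interval, one-sided superiority p-value and incidence rates.

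The cost is two lines of SAP wording and no new data. If completion proves to be dated at follow-up, the stated rates will be somewhat higher than under the present rule.

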10.6.3.5. Dose Adjustment Scheme Endpoints

Dose Adjustment Scheme Endpoints																				
General																				

 The IRT system assigns all randomized treatment doses in accordance with the dose adjustment scheme specified in the protocol. During the study, it is possible for subjects to change randomized treatment doses at both scheduled and unscheduled visits. Sites are instructed to complete an exposure record every time dosing instruction is received from the IRT, with the exception of re-dispensing situations where the subject is instructed to continue using the same randomized treatment. 																				
Daprodustat Doses																				

Sites will enter the dose of daprodustat into exposure records – the daily frequency will be auto-populated for this randomized treatment. The dose steps of daprodustat are shown below:
 
  
 Total Daily Dose	How Administered	
   
 1 mg	single 1 mg tablet	
 
 2 mg	single 2 mg tablet	
 
 4 mg	single 4 mg tablet	
 
 6 mg	single 6 mg tablet	
 
 8 mg	single 8 mg tablet	
 
 10 mg	single 10 mg tablet	
 
 12 mg	two 6 mg tablets	
 
 16 mg	two 8 mg tablets	
 
 24 mg	three 8 mg tablets	
  
	Total Daily Dose	How Administered	1 mg	single 1 mg tablet	2 mg	single 2 mg tablet	4 mg	single 4 mg tablet	6 mg	single 6 mg tablet	8 mg	single 8 mg tablet	10 mg	single 10 mg tablet	12 mg	two 6 mg tablets	16 mg	two 8 mg tablets	24 mg	three 8 mg tablets
Total Daily Dose	How Administered																			
1 mg	single 1 mg tablet																			
2 mg	single 2 mg tablet																			
4 mg	single 4 mg tablet																			
6 mg	single 6 mg tablet																			
8 mg	single 8 mg tablet																			
10 mg	single 10 mg tablet																			
12 mg	two 6 mg tablets																			
16 mg	two 8 mg tablets																			
24 mg	three 8 mg tablets																			

CONFIDENTIAL

201410

Dose Adjustment Scheme Endpoints																							
Darbepoetin Alfa Doses																							

Sites will enter the dose and frequency of each dose of darbepoetin alfa into exposure records. The dose steps of darbepoetin alfa (including the corresponding total 4-weekly doses) are shown below:
																							
	
  
 Total 4-Weekly Dose	Pre-filled Syringe Dose and Frequency	
   
 20 µg	20 µg every 4 weeks	
 
 30 µg	30 µg every 4 weeks	
 
 40 µg	40 µg every 4 weeks	
 
 60 µg	60 µg every 4 weeks	
 
 80 µg	40 µg every 2 weeks	
 
 120 µg	60 µg every 2 weeks	
 
 160 µg	80 µg every 2 weeks	
 
 200 µg	100 µg every 2 weeks	
 
 300 µg	150 µg every 2 weeks	
 
 400 µg	100 µg once a week	
  
	Total 4-Weekly Dose	Pre-filled Syringe Dose and Frequency	20 µg	20 µg every 4 weeks	30 µg	30 µg every 4 weeks	40 µg	40 µg every 4 weeks	60 µg	60 µg every 4 weeks	80 µg	40 µg every 2 weeks	120 µg	60 µg every 2 weeks	160 µg	80 µg every 2 weeks	200 µg	100 µg every 2 weeks	300 µg	150 µg every 2 weeks	400 µg	100 µg once a week
Total 4-Weekly Dose	Pre-filled Syringe Dose and Frequency																						
20 µg	20 µg every 4 weeks																						
30 µg	30 µg every 4 weeks																						
40 µg	40 µg every 4 weeks																						
60 µg	60 µg every 4 weeks																						
80 µg	40 µg every 2 weeks																						
120 µg	60 µg every 2 weeks																						
160 µg	80 µg every 2 weeks																						
200 µg	100 µg every 2 weeks																						
300 µg	150 µg every 2 weeks																						
400 µg	100 µg once a week																						
Assigned Dose at A Scheduled Visit																							

 The assigned dose at a particular visit refers to the dose the subject received at that visit, as recorded in the eCRF. The assigned dose at Visit X is the dose from the earliest exposure record with a start date on or after the Visit X date, but before the Visit X+1 date. 
 For example, the assigned dose at the Week 28 visit is the dose from the earliest exposure record with a start date on or after the Week 28 visit date, but before the Week 32 visit date. 																							
Most Recent Dose Prior to A Scheduled Visit / End of Treatment																							

 The most recent dose prior to a particular visit refers to the dose the subject received in the period directly preceding the visit, as recorded in the eCRF. The most recent dose prior to Visit X is the dose from the latest exposure record with a start date that is on or after the Visit X-1 date and before the Visit X date. 
 For example, the most recent dose prior to Week 28 is the dose from the latest exposure record with a start date that is on or after the Week 24 visit date and before the Week 28 visit date. If a subject permanently stops randomized treatment after Visit X-1 and on or before Visit X, the most recent dose prior to Visit X will be the dose from the subject's final exposure record. 																							
Two Approaches to Dose Adjustment Summaries																							

 The first approach counts all dose adjustments, including dose adjustments related to periods of dose holds (i.e., IRT assignment of a 0-dose). The second approach does not count dose adjustments related to periods of dose holds. However, should the dose that a subject receives following a period of dose hold be different from the dose the subject received before the dose hold, this would still count as a dose adjustment in this approach. 																							

CONFIDENTIAL

201410

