1. PROTOCOL SYNOPSIS

This Phase 3 study will evaluate the efficacy and safety of daprodustat (GSK1278863) compared to recombinant human erythropoietin (rhEPO) in the treatment of anemia associated with chronic kidney disease (CKD) in subjects who are planning to start or who have recently started dialysis. This study will also provide information on daprodustat dosing initiation and titration in subjects initiating dialysis.

Primary Objective/Primary Efficacy Endpoint

The primary objective of the study is to compare daprodustat to rhEPO for hemoglobin (Hgb) efficacy (non-inferiority).

The primary efficacy endpoint will be the mean change in Hgb between baseline and the evaluation period (EP, mean over Weeks 28-52).

Overall Design

- This is a randomized, open-label (sponsor blind), active-controlled, parallel-group, multi-center study in subjects with anemia associated with CKD who are not regularly using erythropoiesis-stimulating agents (ESAs) and who are initiating dialysis.
- This study will comprise three study periods: a screening period (2 weeks*), a 52-week active treatment period, and a follow-up period (4-6 weeks).

* Screening period can be extended by an additional 4 weeks for ultrasound examination, IV iron supplementation and/or vitamin B12 treatment as needed.

- Subjects will be stratified by dialysis type (hemodialysis [HD], or peritoneal dialysis [PD]) and by whether their dialysis start is planned or unplanned (urgent).
- Following stratification, subjects will be randomized 1:1 to receive daprodustat or rhEPO (darbepoetin alfa); all randomized treatments (Section 6.1) will be supplied by GSK.
- Although prior regular ESA use is prohibited, limited ESA use is allowed around the time of dialysis initiation only.
- To ensure consistency of treatment across the study there are protocol-mandated algorithms for dose adjustments of daprodustat and rhEPO, iron management, and rescue.

Type and Number of Subjects

- The study will enroll the following types of subjects with anemia associated with CKD: Planned initiation of dialysis: Subjects who are planning to start chronic dialysis (HD or PD) within the next 6 weeks (from the day of screening).

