7.1. Time and Events Tables and Procedures for Subject Follow-up

Table 6 TIME AND EVENTS TABLE FOR SUBJECTS ON RANDOMIZED TREATMENT

Protocol activity (visits ± 1 week, except Weeks 2 and 4 which are ± 3 days)	Screening Week -2 ¹	Randomization (Day 1)	Weeks 2, 6	Full study visit Weeks 4, 16, 28, 40	Abbreviated study visit Weeks 8, 12, 20, 24, 32, 36, 44, 48	Week 52	Unscheduled	Follow-up Weeks 56-58
Written informed consent ¹⁹	X							
IRT system	X	X	X	X	X		X	X
Entry criteria	X	X						
History: medical, hospitalization, transfusion; demography, height	X							
Weight and estimated dry (target) weight	X	X	X	X	X	X	X	X
SBP/DBP ² , HR ²	X	X ² (triplicate)	X	X	X	X ² (triplicate)	X	X
ECG ³	X	X						
Ultrasound of kidneys and adrenal glands	X ⁴							
Randomized treatment dispensing ¹⁶		X		X	X		X ^{5,6}	
Randomized treatment compliance ¹⁶			X	X	X	X	X ⁷	
Iron therapy, transfusions (record in eCRF, if applicable)		X	X	X	X	X		X
Rescue medication (record in eCRF, if applicable)			X	X	X	X		X
Females only: estradiol & FSH (if required)	X							
Serum pregnancy test ⁸ (FRP only)	X	X		X	X ¹⁷	X	X	X
HemoCue Hgb	X	X	X	X	X	X	X	
Hematology ⁹	X	X		X	Hgb only	X	X	X
Clinical chemistry ⁹	X	X		X		X	X	X
Ferritin, serum iron, UIBC	X ¹	X		X		X		X
Vitamin B12 ¹ , folate	X							
Hepcidin		X		X		X		X

Protocol activity (visits \pm 1 week, except Weeks 2 and 4 which are \pm 3 days)	Screening Week -2 ¹	Randomization (Day 1)	Weeks 2, 6	Full study visit Weeks 4, 16, 28, 40	Abbreviated study visit Weeks 8, 12, 20, 24, 32, 36, 44, 48	Week 52	Unscheduled	Follow-up Weeks 56-58
iPTH		X		X		X		X
Storage biomarkers ¹⁸		X		Wk 28		X		
Kt/V _{urea} for dialysis adequacy ¹⁰				X		X		
Lipids (non-fasting), direct LDL		X				X		
PK Sampling ¹¹				Weeks 4, 8, 12 ¹¹				
Genetics sample ¹²		X						
hsCRP		X		Week 28 only		X		
EQ-5D-5L & VAS ¹³ , SF-36 ¹³		X		Weeks 8,12, 28 only		X		
CKD Anemia Symptoms Questionnaire (CKD-AQ) ^{13,14} , PGI-S ¹³	X	X		Weeks 8,12, 28 only		X		
PGI-C ¹³				Weeks 8,12, 28 only		X		
Healthcare resource utilization (subject reported)	X	X	X	Weeks 4,8,12,16, 20, 24, 28 only		X		X
Hospitalization / kidney transplant (record in eCRF, if applicable)			X	X		X		X
Non-serious AEs, SAEs, AEs of Special Interest, clinical events	X ¹⁵	X	X	X	X	X	X	X
Review concomitant medications	X	X	X	X	X	X	X	X

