
 To evaluate the dose adjustment schemes 	
 Assigned dose by visit and at Day 1, Week 28, Week 52 Most recent dose prior to Week 28, Week 52 Number (%) of subjects with 0, 1, 2 or >2 dose adjustments during the following periods: 
 Day 1 - < Week 28 Week 28 - < Week 52 Day 1 - < Week 52 Number of dose adjustments during the following periods: 
 Day 1 - < Week 28 Week 28 - < Week 52 Day 1 - < Week 52 Time dose held for Hgb \geq12 g/dL

 To further compare daprodustat to rhEPO on BP and BP medication changes 	
 Observed and change from baseline in SBP, DBP and MAP by visit Number of BP medications per subject by visit Change from baseline in the number of BP medications per subject by visit N (%) of subjects who had no change, an increase or a decrease in the dosage or number of BP medications from baseline by visit

 To compare daprodustat to rhEPO on lipid parameters 	
 Observed and % change from baseline in lipid parameters by visit [total cholesterol, direct low density lipoprotein cholesterol (LDL-C), high density lipoprotein cholesterol (HDL-C)]

 To further compare daprodustat to rhEPO on the symptom severity and change 	
 Change from Baseline at Wk 8,12, 28, & 52, by item on the CKD-AQ Shift tables (Baseline to Wk 8, 12, 28, & 52) in PGI-S N (%) of subjects within each PGI-C symptom change level at Wk 8, 12, 28, 52.

 To further compare daprodustat to darbepoetin alfa on HRQoL and Utility score 	
 Change from baseline in Health Utility (EQ-5D-5L) score at Weeks 8,12, & 28 Change from baseline in EQ VAS at Weeks 8, 12, & 28

 To evaluate graphical relationships between exposure parameters and selected efficacy endpoints 	
 Scatter plots of daprodustat PK parameters (Ctau and Cmax) dose normalized to 1 mg vs. percent time in range during EP.

CONFIDENTIAL

201410

Objectives	Endpoints

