An analysis of time to first RBC or whole blood transfusion will be performed as described in Section 10.6.3.4., including a Kaplan-Meier plot.

Dose Adjustment Scheme

See Section 10.6.3 for additional details of dose adjustment scheme endpoints.

The assigned dose by visit will be summarized using mean, standard deviation, minimum, P25, median, P75, and maximum by treatment group.

The assigned dose by visit will also be summarized by treatment group using the number and percentage of subjects assigned to each dose level. Stacked bar graphs displaying assigned dose at all scheduled visits starting with Day 1 will be provided by treatment group.

The median assigned dose by treatment and visit will be displayed graphically for each scheduled study visit using a line plot. The line plot of median assigned dose along with the first and the third quartiles by time will include vertical reference lines to identify the EP as well as the number of subjects by treatment group contributing to each median value.

The following summaries of dose adjustments will be produced twice – the first time counting all dose adjustments, including adjustments related to periods of dose holds (i.e., IRT assignment of a 0-dose), the second time excluding dose adjustments related to periods of dose hold.

The number and percentage of subjects with 0, 1, 2, ..., 10, or >10 dose adjustments will be summarized by treatment group. Summaries will be presented for the following categories of time: Day 1 – < Week 28, Week 28 – <Week 52, and Day 1 – < Week 52.

The number of dose adjustments per subject will be summarized using mean, standard deviation, minimum, P25, median, P75, and maximum by treatment group. Summaries will be presented for the following categories of time: Day 1 – < Week 28, Week 28 – <Week 52, and Day 1 – < Week 52.

The time (in days) that study treatment was withheld for Hgb values ≥ 12 g/dL per subject will be summarized for all subjects and for subjects who had a dose hold using mean, standard deviation, minimum, P25, median, P75, and maximum by treatment group. Summaries will be presented for the following categories of time: Day 1 – < Week 28, Week 28 – <Week 52, and Day 1 – < Week 52.

Summary tables for the dose adjustment scheme endpoints will also be repeated for the following subgroups (see Section 10.10.1 for subgroup definitions):

- Dialysis type at randomization
- Dialysis start manner
- Baseline weight quartiles

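### SAP 10.6.3.5 leaves assigned dose at Week 52 with no data and, depending on two unstated conventions, drops unchanged-dose subjects at Weeks 2 and 6 and prior to Weeks 4 and 8

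*SAP*

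**What the plan says.** SAP 10.6.3.5 gives two rules for dose by visit.

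- Assigned dose at Visit X is taken from the "earliest exposure record with a start date on or after the Visit X date, but before the Visit X+1 date".
- Most recent dose prior to Visit X is taken from the "latest exposure record with a start date that is on or after the Visit X-1 date and before the Visit X date".

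Neither rule looks back to a record that started before its window. There is one fallback, in the second rule only: if a subject permanently stops between the two visits, "the most recent dose prior to Visit X will be the dose from the subject's final exposure record".

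The same section has sites open an exposure record at each IRT dosing instruction, "with the exception of re-dispensing situations where the subject is instructed to continue using the same randomized treatment".

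SAP 2.2 and Protocol Appendix 2 list the exploratory endpoint "Assigned dose by visit and at Day 1, Week 28, Week 52". SAP 8.1.3.2 adds by-visit tables, a median assigned-dose plot and a median most-recent-dose plot laid over mean Hgb. It also states: "Stacked bar graphs displaying assigned dose at all scheduled visits starting with Day 1 will be provided by treatment group".

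In Protocol Table 6, repeated in SAP 10.2.1.1, the row "Randomized treatment dispensing" is blank at Weeks 2, 6 and 52. The IRT row is marked at Weeks 2 and 6 and blank at Week 52.

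**The concern.** SAP 10.6.3.5 introduces both quantities as the dose a subject was receiving, at the visit or in the interval just before it. The derivation instead asks whether a new record began in a particular interval. A subject who stays on one dose is on treatment, yet can have no value.

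The loss would not be random. Under the footnotes to the dose adjustment scheme in Protocol Appendix 3, the rules that reach Weeks 2 and 6 are those for a change in Hgb of more than 1 g/dL over 2 weeks, Hgb below 7.5 g/dL, and Hgb of 12 g/dL or more. Subjects with a new dose there are fast or extreme responders. The darbepoetin booster at those weeks is also tied to a fast fall or very low Hgb. A plot of median dose over mean Hgb would then pair the dose of a selected few with an Hgb mean not limited to them.

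The Protocol Synopsis gives the displays a purpose: "This study will also provide information on daprodustat dosing initiation and titration in subjects initiating dialysis".

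**Working it through.** The plan states no figure to reproduce. The check applies the two rules to the schedule for a subject who stays on treatment and never changes dose.

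**Inputs**

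- Visits (Protocol Table 6): Day 1, Weeks 2, 4, 6, 8, then every 4 weeks to 52, then follow-up from Week 56.
- Dispensing (Table 6): Day 1, Weeks 4 and 8, then every 4 weeks to 48.
- IRT contact on treatment (Table 6): the dispensing visits plus Weeks 2 and 6.
- 150 subjects per arm (Protocol 4.2); up to about 30% permanent stops before Week 28 (Protocol 9.2.1).

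**Step 1. Which values are missing for an unchanged dose**

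Assigned dose at Week 52 needs a record starting in [Week 52, follow-up). Assigned dose at Week 2 and most recent dose prior to Week 4 both need one starting in [Week 2, Week 4). Assigned dose at Week 6 and most recent dose prior to Week 8 both need one starting in [Week 6, Week 8).

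| Visit grid | A record opens at | Assigned dose missing at | Most recent dose missing prior to |
|---|---|---|---|
| With Weeks 2 and 6 | each dispensing visit | Weeks 2, 6, 52 | Weeks 4, 8 |
| With Weeks 2 and 6 | each IRT contact, maintained doses included | Week 52 | none |
| Four-weekly only | each dispensing visit | Week 52 | none |
| With Weeks 2 and 6 | dose changes only | every visit after Day 1 | every visit from Week 4 |

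Week 52 is empty in every row. The rest depends on the row, and the SAP does not say which applies.

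**Step 2. Size under the first row**

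The documents give no rate of dose change, so 5% to 30% in the Week 2 window is an assumption.

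- Assigned dose at Week 2, contributors per arm: 150 × 0.05 = 7.5 up to 150 × 0.30 = 45. Missing: 142.5 down to 105.
- Prior to Week 4, stoppers also contribute. With a constant hazard, the 2-week stop probability is 1 − 0.70^(2/28) = 0.025.
- At 5%: 7.5 changers and 150 × 0.95 × 0.025 = 3.6 stoppers, so changers are 7.5/11.1 = 68%.
- At 30%: 45 changers and 150 × 0.70 × 0.025 = 2.6 stoppers, so changers are 45/47.6 = 94%.

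**Step 3. What selection could do to a displayed mean**

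Assume daprodustat starting doses of 4, 2 and 1 mg in 30%, 50% and 20% of subjects, with 10% moving one step at Week 2.

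- Unchanged mean: 0.3×4 + 0.5×2 + 0.2×1 = 2.4 mg.
- Mean after an increase: 0.3×6 + 0.5×4 + 0.2×2 = 4.2 mg.
- Mean after a decrease: 0.3×2 + 0.5×1 + 0.2×0 = 1.1 mg.

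| Share of changes that are increases | Mean shown by the rule (mg) | Mean of whole arm (mg) |
|---|---|---|
| 20% | 0.2×4.2 + 0.8×1.1 = 1.7 | 0.9×2.4 + 0.1×1.7 = 2.3 |
| 50% | 0.5×4.2 + 0.5×1.1 = 2.65 | 0.9×2.4 + 0.1×2.65 = 2.4 |
| 80% | 0.8×4.2 + 0.2×1.1 = 3.6 | 0.9×2.4 + 0.1×3.6 = 2.5 |

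The distortion can go either way and is small when increases and decreases balance. This is an illustration, not an estimate.

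**The case against.** The strongest reply is that only Week 52 is certain, and this stands.

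- **Recording.** The SAP's default is a record at every IRT instruction, and Table 6 shows IRT contact at Weeks 2 and 6. Treating a maintained dose there as the excepted case is an inference. Protocol 6.6 supports it for Week 2, where no compliance check is made if the dose is unchanged, but does not name Week 6. The eCRF instructions are not in the documents.
- **Visit grid.** Protocol Appendix 3 uses *study visit* for four-weekly visits, and the SAP's worked examples use Weeks 24, 28 and 32. Against that, Weeks 2 and 6 are columns in the SAP's own schedule, and SAP 8.1.3.2 plots all scheduled visits.
- **Mitigation.** Most recent dose prior to Week 52 is already listed. Counts of dose adjustments and time on hold do not use these rules. The line plots print the contributing n, so a collapse would be visible.

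A reader might infer that dose displays for the whole first 8 weeks show only just-adjusted subjects. The documents do not support that: with a record at each dispensing visit, assigned dose is filled at Day 1 and Weeks 4 and 8, and most recent dose prior to Weeks 2 and 6.

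A reader might also infer from the 126-day row in the compliance table of SAP 10.6.2.4 that records spanning several visits are expected. That row belongs to an open-ended lookup and shows no such expectation. From Week 4 to Week 48 dispensing is four-weekly, and Protocol Section 7 asks for visits no more than 5 weeks apart.

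**Conclusion.** The derivation is wrong as written, with limited reach. The Week 52 gap is firm: about 300 randomized subjects, none with a source record for a listed endpoint, whatever the grid or recording convention.

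The gap at Weeks 2 and 6, and prior to Weeks 4 and 8, holds only if those weeks are in the grid and no record is opened for a maintained dose. Then these points reflect mainly subjects just adjusted, plus permanent stoppers for the two *prior to* values. Other visits are filled provided a record is opened at each dispensing visit. How many subjects would be missing cannot be stated from the documents; the 7.5 to 45 contributors per arm rest on an assumed change rate.

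The endpoints are exploratory with no testing planned. This is worth correcting, but it is not a threat to the trial's conclusions.

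**What to change.** 1. Drop assigned dose at Week 52 from SAP 2.2 and the by-visit displays, record the change in SAP 2.1, and rely on the most recent dose prior to Week 52.
2. State which visits form the X−1, X, X+1 grid, and whether Weeks 2 and 6 belong to it.
3. Keep the current window where a record starts inside it, so that a new dose dispensed late under Table 6 footnote 16 is still captured. Otherwise, for subjects still on randomized treatment, carry forward the dose on the exposure record in effect at the visit, including IRT zero-dose records.
4. Apply the same carry-forward to most recent dose, keeping the existing fallback for permanent stoppers.
5. Show the number with missing dose by visit and arm.

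The cost is a few lines of SAP text and a small change to the derivation. With carry-forward, every on-treatment subject has a value at Weeks 2 and 6 and prior to Weeks 4 and 8, from data already collected.
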